## **Recruitment, Screening, and Enrollment**

**Client participants.** Designated WCCMH personnel will identify client participants who meet criteria for study inclusion based upon DSM SSPD diagnosis and endorsement of suicide ideation and/or attempt within 3 months per documentation of the C-SSRS. Case managers will be notified if their client(s) meet criteria and will be prepared with instructions by the research team (see scripts) on how to present the study given clients' potential eligibility. Clients who are interested to learn more will be instructed to either: 1) reach out to research staff (RS) via phone, or, 2) give consent for the case manager to give the potential participant's contact information to RS so they can be contacted via phone and learn of next steps (eligibility, consent, enrollment, assessment). RS will schedule an in-person meeting with clients who are interested in learning more about the at WCCMH (coordinating with an already scheduled appointment with a provider). In this meeting, RS will describe the study (see scripts) and review the informed consent form. If consent is obtained, the screening tool will be administered to determine eligibility for enrollment (approximately 15 minutes long). Screening will involve use of The Mini International Neuropsychiatric Interview (MINI) to confirm a SSPD based upon criteria of the DSM-5. A 3-month history of SI/A will be confirmed using the C-SSRS. Lastly, the Wide Range Achievement Test 4 (WRAT-4) will be administered to confirm at least a 6th grade reading level in English given use of CBSPp materials.

## **Procedures After Enrollment**

**Client participants in open trial of Aim 1.** Clients participating in the open trial of Aim 1 will:

1. Complete a 1-hour survey following enrollment (not a separate visit), including questions about personal characteristics, symptoms of psychosis, depression, suicide thoughts and suicide attempt.
2. Attend weekly one-on-one therapy sessions with a trained provider for up to 10 weeks. Our research staff will set this and therapy sessions will take place at Washtenaw County Community Mental health at your convenience. Therapy sessions will be focused on improving thoughts of suicide and preventing suicide attempt. All therapy sessions will be audio recorded so we can check that therapists are correctly giving this treatment.
3. Complete a 1-hour survey approximately in 1-month, 3-months, and 5-months. Surveys will be focused on experiences with symptoms of psychosis, depression, suicide thoughts and suicide attempt.
4. Use a treatment website that we will provide between therapy sessions with short videos to help you practice skills you will learn in treatment.
5. Attend a 1-hour interview with research staff at the end of the study which will be audio recorded and include questions about experiences in the study.

If client participants refuse to participate after determined to be eligible, enrolling in the study, being assigned to a provider, and/or starting study activities (surveys and/or treatment), they will be removed from the study and thanked for their time.

If a client participant leaves WCCMH services (e.g., moves, ends services, switches to different service provider) during the study, their participation in the study will end.

Client participant attendance will be tracked as one of our goals is to learn more about acceptability and feasibility of the intervention. While 10 sessions are what providers will be trained to deliver, clients may choose not to attend all sessions. It is important to note that

there will be no consequences for not attending sessions; participants can remain as active as they choose to be with treatment and survey completion.

If a provider leaves during the study and/or during the process of delivering CBSPp with a client participant, we will re-assign the client(s) to a different therapist who has been trained in CBSPp. If needed, we train additional providers in preparation for resuming treatment with client participants whose previous provider left.

**Cognitive Behavioral Suicide Prevention for psychosis (CBSPp).** Clients in the Aim 1 Open Pilot Trial treatment group (CBSPp) will attend individual therapy sessions with a trained provider (10 weeks/10 sessions) in addition to standard WCCMH care (e.g. individual treatment, family services, case management, and medication management). Sessions will be audiotaped and providers will administer the C-SSRS to assess for SI/A in each visit for risk management. CBSPp was developed as a 24-week series of individual therapy sessions with a clinician in a structured protocol, and modified to be 10 weeks in Aim 1 of this study (stakeholder phase of Aim 1 prior to open pilot trial). Cognitive and behavioral techniques are implemented systematically to address cognitive (information processing biases, appraisals, and schemas) components from the SAMS theoretical model (see **Table 1**). The goal is to develop broad-minded attention, balanced appraisals, and alternative schemas about the self, world, and the future resulting in exit from suicide schemas. The three cognitive components of SAMS have been tested empirically, though not within a CBSPp trial.

Table 1. Cognitive components of CBSPp Mapped onto Tasks and Goals in Treatment		
Cognitive Component	Task	Goal
Information processing biases	Attention to imagery and stimuli, guided relaxation, and broad-minded affective coping	Improve attentional control, positive affect, relaxation, and breathing (Target: Information processing biases)
Appraisals	Cognitive restructuring to identify implicit and explicit thoughts, challenging appraisals, and behavioral experiments	Shift negative appraisals (Target: appraisals)
Schemas	Guided imagery and systematic questions to promote the development of positive beliefs and improvements in self-esteem, and cognitive and affective responding.	Deactivate suicide schemas and adopt new beliefs and schemas of situations, the self, and future (Target: schemas)

Tarrier et al., 2013

CBSPp is structured to begin with an assessment phase followed by a treatment phase in which numerous techniques and strategies are used to address information processing biases, negative appraisals, and suicide schemas. Assessment phase sessions involve explorations of psychiatric symptoms, history of suicide ideation and attempt, family history of psychiatric illness, recent stressful life events, risk for suicide, recovery goals, protective factors, inhibitory factors, coping skills, social support and sense of defeat, entrapment, and hopelessness; all of which will inform the treatment delivery. Throughout assessment, the clinician begins to identify suicide-related information processing biases, appraisals, and schemas. After assessment, techniques and strategies are used in-session and assigned in homework to address information processing biases, negative appraisals, and suicide schemas. Exits from suicide schema occur as evidence of resilience and the cognitive processes involved in these exits are identified and reinforced in the treatment process. While CBSPp is a promising intervention with encouraging preliminary data, it requires protocol and implementation modifications to increase its utility in community mental health settings.

## Assessment

**Aim 1 Open pilot trial Quantitative data.** Clients will complete comprehensive assessments at baseline (T1), mid-test (midpoint of total CBSPP sessions; T2), post-test (endpoint of CBSPP sessions; T3), and follow-up (3 months after CBSPP session endpoint; T4). Measurement shown below in Table 3.

Construct	Instrument(s)	Time	Reporter
Aim 2a: To assess whether modified CBSPP is associated with reductions in SI/A (primary outcome), symptoms of psychosis, depression, and service use over time.			
SI/A	Columbia Suicide Severity Rating Scale (CSSRS) 	T1,T2,T3,T4	CT, RS score
Psychosis	Positive and Negative Syndrome Scale (PANSS) 	T1,T2,T3,T4	CT, RS score
Depression	Calgary Depression Rating Scale (CDRS) 	T1,T2,T3,T4	CT, RS score
Aim 2b: To assess whether modified CBSPP is associated with clinical and cognitive improvements over time.			
Clinical	Hopelessness	Beck Hopelessness Scale (BHS) 	T1,T2,T3,T4
	Defeat	Defeat Scale 	T1,T2,T3,T4
	Entrapment	Entrapment Scale 	T1,T2,T3,T4
	Social support	Quality of Life 	T1,T2,T3,T4
	Coping	Coping in Stressful Situations Inventory (CSSI) 	T1,T2,T3,T4
Cognitive	Information processing biases	Modified Stroop task 	T1,T2,T3,T4
	Appraisals	Resilience Appraisals Scale (RAS)  Reappraisal Subscale of Emotion Regulation Questionnaire (ERQ) 	T1,T2,T3,T4
	Schemas	Suicide Concept Sort Task (SCT) 	T1,T2,T3,T4
			CT
Key: T1 = baseline; T2= mid-test; T3= post-test; O= ongoing; CT= clients; RS score = research staff score ratings as this is a clinical interview and not a self-report measure.			

**Aim 1 Open Pilot trial Qualitative assessment.** We will systematically evaluate the modified CBSPP using in-depth face-to-face qualitative interviews with all clients in the open pilot trial. Topics will focus on: 1) perceptions about their experience receiving the treatment, feedback regarding treatment impact and observed mental health outcomes, experiences with the added engagement enhancers, and factors impacting possible sustainability of maintaining the treatment at community mental health over time.

## Statistical Design and Analysis

**Aim 1 open pilot quantitative data analysis.** A focus of Aim 1's open pilot is to implement the CBSPP treatment and assessments in preparation for potential modifications prior to Aim 2. We will preliminarily explore outcomes (SI/A, symptoms of psychosis, depression, emergency/hospital service use, hopelessness, defeat, entrapment, information processing biases, appraisals, and schemas) in preparation for Aim 2. Given the open pilot is small in size (n=8 clients), we don't have power to detect changes over time in Aim 1. Therefore, quantitative data will be examined at the univariate and bivariate level for distributions and associations between variables. Measures of dispersion (mean, standard deviation, variance, range) and distribution (kurtosis, skewness) will be computed. Scatterplots will be generated to examine linearity and outliers for bivariate relationships using Chi-Square analysis (categorical variables), analysis of variance (ANOVA; scaled variables), and paired samples t-tests (continuous variables) in SPSS28.

**Aim 1 open pilot qualitative data analysis.** Qualitative in-depth interviews data were transcribed and coded using Dedoose. Transcripts were independently coded by two research assistants (RAs) in preparation for codebook development using an open coding technique to generate themes across qualitative questions (Saldana, 2016). Grounded theory methods were utilized for analysis (Charmaz, 2014). The PI met with both RAs to discuss emerging themes after a first round of coding and agreed upon a final codebook. Both RAs completed a second round of coding using the final codebook and the PI resolved any disagreements to achieve inter-coder consistency. Themes were ultimately organized into a final framework and the following strategies for rigor (Padgett, 2016) were included in the study: 1) triangulation, specifically analytic triangulation (more than one coder), 2) audit trail, and 3) member checking with stakeholder participants (i.e., in provider, peer, and client meetings).

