**Specific Aim 1: To modify CBSPp for clients with schizophrenia spectrum and other psychotic disorders (SSPD) receiving CMH services.** We will develop the provider training, client engagement enhancers, and conduct in-depth qualitative interviews to evaluate CBSPp materials and delivery protocol with stakeholders, including ≈15 adults with SSPD and suicidal ideation and/or attempt (SI/A) within 3 months of screening and ≈10 CMH staff, providers, directors and leaders. Qualitative data will be analyzed and subsequently presented to a panel of scholarly experts in suicide, psychosis, intervention, and implementation science for input. A systematic process will guide CBSPp modifications, refinement of the provider training and client engagement enhancers, and an open pilot trial will be conducted with 8 clients and 2 providers. Open pilot findings and explorations of organizational impact of implementation will be discussed with the expert panel, followed by any additional modifications from feedback and lessons learned.

**Specific Aim 2: To evaluate the feasibility and preliminary effectiveness of modified CBSPp in comparison to services-as-usual (SAU).** Adults with SSPD and SI/A within 3 months of screening (n=60) will be enrolled and randomized to CBSPp or SAU. A 4-wave design will include quantitative assessments at baseline (T1), mid-test (T2), post-test (T3), and follow-up (T4) with in-depth qualitative interviews at T4 for a random sample of adults in the CBSPp group (n=10). Providers (n=8) will be trained to deliver CBSPp and be assessed T1-T4 to evaluate the implementation process, including in-depth qualitative interviews at T4. We will monitor fidelity, acceptability, usability, and feasibility of the modified CBSPp.

**Aim 2a: To assess whether modified CBSPp is associated with reductions in SI/A (primary outcome), symptoms of psychosis, depression, and emergency/hospital service use over time.** Compared to SAU, the CBSPp group will experience significant reductions in SI/A

(H1), symptoms of psychosis (H2), symptoms of depression (H3), and emergency/hospital service use (H4).

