#### **Additional Procedural Information**

**Service use tracking.** Service use will be tracked in an electronic medical record and designated staff of WCCMH will access this information and de-identify it for linkage with collected participant data in the study (from assessments). Participants will be linked to their study ID number in the process of de-identifying data for the research team. Clinical data that will be obtained from the participant's CMH medical record, as described in the consent, will include attendance and service use at CMH, frequency and nature of emergency room visit documentation, and frequency and nature of inpatient hospitalization documentation. More specifically, details of CMH services (frequency and duration of visits both scheduled and attended with therapist, psychiatrist, case manager, assertive community treatment team, and crisis residential service team) and community services (emergency room visits and inpatient hospitalizations) engaged in.

**Provider CBSPp supervision.** The PI and [name] (including consultation with [name] as needed) will supervise provider delivery of CBSPp through group videoconference (2-4 hours per month) and will be available as needed for clinical issues that may arise (see *Protection of Human Subjects*). Supervision will focus on CBSPp delivery, review of sessions, clinical care, fidelity, and implementation. Imbedded in supervision will also be identification and management of adverse events as a refresher to reinforce the study's safety protocol.

**Provider competence and CBSPp fidelity.** Throughout the open pilot, providers will self-rate fidelity using a checklist after each session. Also, 20% of audiotaped sessions will be randomly selected for blind rating by two established experts currently assessing CBT fidelity within [name] NIMH-funded projects.

**Feasibility.** We will track the number of: 1) calls made and received with potential participants, 2) signed informed consents, and 3) eligible participants after screening. We will determine feasibility of CBSPp by: 1) session attendance, 2) CMH service use, and 3) fidelity ratings. An element of feasibility is the ability to recruit participants in the proposed timeframe.

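### With 8 clients, the chi-square approximation behind the only categorical method named in the pilot plan cannot be relied on; use an exact test, or counts with exact intervals

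*Combined protocol and SAP*

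**What the plan says.** Statistical Design and Analysis, in the paragraph on open pilot quantitative data, gives the sample size and concedes low power: "Given the open pilot is small in size (n=8 clients), we don't have power to detect changes over time in Aim 1". It continues: "Therefore, quantitative data will be examined at the univariate and bivariate level for distributions and associations between variables". The method for categorical data is then named: "for bivariate relationships using Chi-Square analysis (categorical variables"). Analysis of variance and paired t-tests are named in the same sentence, but for scaled and continuous variables. Specific Aim 1 confirms the size: "an open pilot trial will be conducted with 8 clients and 2 providers".

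Nowhere do the documents name an exact test, a continuity correction, a minimum expected count or a counts-only rule for categorical data. They also do not list which variables will be cross-tabulated. Two places suggest candidates. The enrolment survey is described under Procedures After Enrollment as "including questions about personal characteristics, symptoms of psychosis, depression, suicide thoughts and suicide attempt". The service-use extract under Additional Procedural Information includes "frequency and nature of emergency room visit documentation".

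**The concern.** The chi-square test takes its p-value from a large-sample distribution that needs reasonably large expected counts. With 8 clients those counts are out of reach whichever variables are chosen, and this is known before any data are collected. The plan responds to low power for change over time by turning to bivariate associations. Low power, however, is a separate matter from a p-value that can be too small.

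What is at stake is limited. A chance coincidence in a sparse table could be reported as a significant association. Specific Aim 1 says "Open pilot findings and explorations of organizational impact of implementation will be discussed with the expert panel", and further modifications follow from that discussion, so such a result could be passed on. That sentence does not mention p-values, and the pilot has no stated alpha, hypothesis test or decision rule.

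**Working it through.** The plan gives no power, alpha or derived sample size for the pilot, so there is no figure of its own to reproduce.

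**Inputs.** N = 8 clients (Specific Aim 1; Statistical Design and Analysis). Method: chi-square, read here as uncorrected Pearson because no correction is named. Assumed: two-sided 0.05, and one record per client at one wave. All tables below are hypothetical.

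**1. Expected counts.** Expected count = row total × column total / 8. Let r and c be the smaller row and column totals of a 2x2 table, each at most 4.
- Smallest expected count: rc/8 ≤ 4×4/8 = 2.
- The two mixed cells, r(8−c)/8 and (8−r)c/8, are at most 4×7/8 = 3.5. Only the fourth cell can reach 5, so at least three are below 5.
- In a 2x3 table the smallest row total is at most 4 and the smallest column total at most 2, so the smallest expected count is at most 4×2/8 = 1.
- Missing data lower these figures.

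**2. Single tables.** Pearson X² = 8 × [Σ n²/(row total × column total) − 1]. For 2x2 tables this equals 8(ad−bc)²/(product of the four margins). The exact p-value sums the probabilities, given the margins, of all tables no more likely than the one observed.

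| Margins | Table | X² (df) | Pearson p | Yates p | Exact p |
|---|---|---|---|---|---|
| 3/5 by 4/4 | 3,0 / 1,4 | 8×12²/(3×5×4×4) = 4.80 (1) | 0.028 | 0.144 | 2×4/56 = 0.143 |
| 2/6 by 3/5 | 2,0 / 1,5 | 8×10²/(2×6×3×5) = 4.44 (1) | 0.035 | 0.206 | 3/28 = 0.107 |
| 1/7 by 1/7 | 1,0 / 0,7 | 8×7²/(1×7×1×7) = 8 (1) | 0.005 | 0.225 | 1/8 = 0.125 |
| 1/7 by 1/1/6 | 1,0,0 / 0,1,6 | 8×(1 + 1/7 + 36/42 − 1) = 8 (2) | 0.018 | not applicable | 2/8 = 0.250 |
| 2/6 by 2/2/4 | 2,0,0 / 0,2,4 | 8×(1 + 4/12 + 16/24 − 1) = 8 (2) | 0.018 | not applicable | 2/28 = 0.071 |

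**3. Level of uncorrected Pearson in 2x2 tables at 0.05.** There are ten pairs of margins, counting transposes once.
- Given both margins: 0.143 (3/5 by 4/4), 0.125 (1/7 by 1/7) and 0.107 (2/6 by 3/5). In the other seven pairs it is 0 to 0.036.
- Row sizes fixed, worst case over a common probability: 0.049 (1/7), 0.055 (2/6), 0.070 (3/5) and 0.070 (4/4). For example, in 4/4 with probability 0.5, 18 of the 256 equally likely outcomes reject: 18/256 = 0.070.
- Neither margin fixed, worst case, with both probabilities 0.5: weight the rejecting outcomes by the number of ways to form each row split. (70×18 + 112×18 + 56×14 + 16×2)/256² = 4092/65536 = 0.062.

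**4. Alternatives.**
- Yates: no 2x2 table has Yates p<0.05 with Fisher p≥0.05.
- Fisher: can reach p<0.05 in three of the ten margin pairs only (2/6 by 2/6, 0.036; 3/5 by 3/5, 0.018; 4/4 by 4/4, 0.029). Its worst-case level with row sizes fixed is 0 to 0.011.
- Exact binomial 95% intervals: 0/8 gives 0% to 37%, 2/8 gives 3% to 65%, and 4/8 gives 16% to 84%. For 0/8 the upper limit is 1 − 0.025^(1/8) = 0.37.

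**The case against.** The best defence is that little harm is shown. In a single-arm pilot a cross-tabulation of client characteristics usually fixes neither margin, and the worst-case 2x2 level is then 0.062 against a nominal 0.05. The larger levels arise only after conditioning on both margins, in three of ten pairs. Fisher's test is no neutral benchmark either: it is very conservative at this size, so part of the disagreement reflects its discreteness. With 1/7 by 1/7 margins it cannot reach 0.05 whatever the data. All this stands, and it is why the point is minor.

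It is also fair that the plan does not say the test is uncorrected, and that Yates would remove the 2x2 fault. But Yates is not named and does not apply to 2x3 tables.

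The tables are hypothetical: most instruments are scales or tasks, and service use is recorded largely as frequencies and durations. Recent suicidal ideation or attempt is required for entry, so that combined variable is constant at baseline. Attempt alone and personal characteristics can still vary, and the bound on expected counts holds for any choice. Pooling the four waves would give up to 32 records, but records from one client are not independent.

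Finally, whether an exploratory pilot should test at all applies equally to the analysis of variance and t-tests in the same sentence. That is a fair wider question. It does not make the chi-square approximation adequate.

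**Conclusion.** The point holds and is minor. Chi-square is the only method named for categorical variables, and the ceiling on the smallest expected count (2 in a 2x2 table, 1 in a 2x3 table) is arithmetic that depends only on there being 8 clients. The comparison of p-values rests on three assumptions: an uncorrected Pearson test, a two-sided 0.05 threshold and one record per client.

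Under these, overall inflation in 2x2 tables is modest, and the misleading results are confined to particular sparse tables, where a Pearson p-value of 0.005 to 0.035 can correspond to an exact value of 0.071 to 0.250. No stated conclusion of the pilot depends on such a p-value, so the effect is limited to how exploratory associations are reported.

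**What to change.** Replace chi-square for associations between clients at a single wave with one of two options:

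- Fisher's exact test, with the Freeman-Halton extension for tables larger than 2x2. It controls the error rate but will seldom reject with 8 clients.
- Counts with exact binomial 95% intervals and no test. This avoids Fisher's conservatism and shows directly how little 8 clients can establish.

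It would help to state which variables are cross-tabulated and at which wave, though the point does not depend on that. The cost is one sentence in the analysis plan, with no new data and no change to study conduct. The qualitative paragraph is already in the past tense ("Qualitative in-depth interviews data were transcribed and coded using Dedoose") while the quantitative text is in the future tense, so the documents do not settle whether pilot data have been seen. If they have, label the change as post hoc.
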